6.6 Baseline Definition

The Baseline visit (Day 0) will take place once the results of Screening assessments are obtained, suggesting that the subject is eligible for entering the study. During this visit, those subjects who qualify for entering the study will be randomized to one of the study arms in a ratio of 1:1.

6.7 Derived and Transformed Data

6.7.1 Baseline Age

Subject's age in years will be calculated based on the date of the Baseline Visit date using the following formula:

Age (years) = FLOOR ((INTCK ('month', Date of Birth, Date of Baseline Visit) - (DAY(Date of Baseline Visit) < MIN(DAY(Date of Birth), DAY (INTNX ('month', Date of Baseline Visit, 1) - 1))) /12)); where:

- FLOOR () is a SAS function that returns the largest integer that is less than or equal to the argument.
- INTCK () is a SAS function that returns the number of interval boundaries of a given kind that lie between two dates, times, or datetime values.
- DAY () is a SAS function that returns the day of the month from a SAS date value.
- INTNX () is a SAS function that increments a date, time, or datetime value by a given time interval, and returns a date, time, or datetime value.

6.7.2 Study Day

Day 1 is defined as the day after the baseline when the subject will receive the first dose.

- For a visit date on or after the date of the first dose:
Study Day = (date of interest – date of first dose) + 1
- For a visit date before the date of the first dose:
Study Day = (date of interest – date of first dose)

6.7.3 Multiple Assessments

No multiple assessment for same visit are scheduled.

6.7.4 Handling of Missing Data & Sensitivity Analysis

For the primary and secondary analysis no missing values will be imputed. A sensitivity analysis will be performed by Multiple Imputation Regression Analysis using the following factors: treatment, age, gender, race, baseline IGA, baseline CEA, baseline PSA, smokers/non-smokers and the results of the same variable from previous visits.

6.7.5 Missing Start and Stop Dates for Prior and Concomitant Medication

Start date:

- If start date is completely missing, start date will not be imputed.
- If (year is present, and month and day are missing) or (year and day are present, and month is missing), set month and day to January 1.
- If year and month are present and day is missing, set day to the 1st day of month.

Stop date:

- If end date is completely missing, end date will not be imputed.
- If (year is present, and month and day are missing) or (year and day are present, and month is missing), set month and day to December 31st.
- If year and month are present and day is missing, set day to the last day of month.

6.7.6 Safety Parameters

Safety and tolerability endpoints will consist of all adverse events (AEs) reported during the study duration from the date of randomization through Week 12 (End of Study Visit).

Specific AEs are defined below.

Treatment-Emergent Adverse Events (TEAE): Any AE with onset after the first dose of study medication through 56 days after the last dose of study medication.

Serious Adverse Event (SAE): An AE occurring at any dose that results in any of the following outcomes: death, a life-threatening AE, in-patient hospitalization or prolongation of existing hospitalization, a persistent or significant disability/incapacity, or a congenital anomaly/birth defect.

Associated with Use of the Study Drug: There is a reasonable possibility that the experience may have been caused by the study drug. If the Investigator does not know whether or not study drug caused the event, then the event will be handled as “related to study drug” for reporting purposes. The determination of whether an AE is related to study drug is as follows:

- Related: The AE has a missing, unknown, possible, probable or definite relationship to the study medication.
- Not related: The AE is unlikely or definitely unrelated to the study drug.

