
STUDY DESIGN:
	
This is a Prospective, Vehicle Controlled, Double Blind, Multicenter, Randomized Phase II trial, comparing the effect of twice daily B244 application for 8 weeks vs. vehicle application on treatment of mild to moderate rosacea.
 
At Screening and Baseline:
 
• All subjects must have diagnosis of mild to moderate Rosacea.• Subjects must have IGA score of 2-3 and CEA score of 2-3 in order to qualify for the study.• After screening and recruitment, participants will be randomized to active or vehicle application for 8 weeks.• Subjects will apply a total of 4 pumps of IP per application to the face twice-a-day• Randomization will be 1:1 B244 to Vehicle.• Subjects will be provided with cleanser and moisturizer to use for the duration of the study• All B244 randomized subjects will be treated at the dose of 4×10^9 cells/ml via spray application• Screening period will occur at Days -21 to -1• Washout will occur after Screening visit (Days -14 to -1)• Randomization will occur during the baseline visit for the study• Efficacy will be assessed using Investigator Global Assessment (IGA) score, Clinician's Erythema Assessment (CEA) score, Patient Self-Assessment (PSA) score and patient reported Skindex 16.• Clinical assessments of response to treatment will be made at Week 1 (Day 7), Week 4 (Day 28), and Week 8 (Day 56)• At Baseline visit, subjects will receive a kit containing the drug product. Each bottle will be used for 2 weeks. At Week 4, subjects will return the used bottles from the kit and will be issued a new kit of drug product to be used from Week 4 through Week 8.• Subjects will stop applying investigational product at Week 8 and will return investigational product at that visit.• Subjects will come back for a 4-week post-treatment follow up visit at Week 12 (Day 84).
----------------------	--

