12 SAFETY DATA COLLECTION, RECORDING AND REPORTING

The Investigator will monitor each subject for clinical evidence of adverse events on a routine basis throughout the study. The Investigator will assess and record any Adverse Event (AE) in detail including the date of onset, description, severity, time course, duration and outcome, relationship of the adverse event to investigational product, an alternate etiology for events not considered “related” or “probably related” to investigational product, final diagnosis, if known, and any action(s) taken. For AEs to be considered intermittent, the events must be of similar nature and severity and each intermittent AE will be reported separately. AEs and SAEs, whether in response to a query, observed by site personnel, or reported spontaneously by the subject will be recorded, monitored and followed-up until the resolution (or until the Investigator deems the event to be stable/chronic).

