12.1 Definitions

12.1.1 Adverse Event

An AE is defined as any untoward medical occurrence in a Subject or clinical investigation subject administered a pharmaceutical product and which does not necessarily have a causal relationship with this treatment. An AE can therefore be any unfavorable and unintended sign (including an abnormal laboratory finding), symptom, or disease temporally associated with the use of a medicinal (investigational) product, whether or not the event is considered causally related to the use of the investigational product.

Such an event can result from use of the drug as stipulated in the protocol or labeling, as well as from accidental or intentional overdose, drug abuse, or drug withdrawal. Any worsening of a pre-existing condition or illness is considered an AE. If a new rosacea sign or symptom or worsening of a rosacea sign or symptom was believed by the investigator to be related to the investigational product and not the disease, then it will be recorded as an AE. Clinically significant abnormalities are to be followed to resolution (i.e., become stable, return to normal, return to baseline, or become explainable). Laboratory abnormalities and changes in vital signs are considered to be AEs only if they necessitate therapeutic medical intervention, and/or if the Investigator considers them to be AEs.

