12.4 Adverse Event Collection Period

Adverse Event Collection Period starts with the Screening visit once the ICF has been signed through the follow-up visit (week 12). Any AE/SAE prior to the Screening visit will be considered past medical history (PMH).

SAE(s) that are observed or spontaneously reported during the subject's participation in the trial will be captured and monitored until the Investigator deems the event to be chronic or not clinically significant or the subject to be stable.

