Withdrawal and Early Discontinuation	A subject may voluntarily withdraw from the study at any time and for any reason without prejudice to his or her future medical care. The Investigator, Sponsor, or Medical Monitor may also withdraw a subject at any time if it is medically necessary or in the interest of subject's safety. If a subject discontinues prematurely, the Investigator will perform Early Termination (ET) visit, capturing the reason for discontinuation. Further details are provided in section 5.2 & 5.3 of the Protocol RB244-001 v4.0.	
Prohibited Concomitant Medication	Prohibited Therapies are those medicinal products and treatment methods that are not allowed during the study period and within the timeframes specified in the section 8.1 of the Protocol RB244-001 v4.0.	
Study Drug	Study drug includes Test and Placebo drug products. The Sponsor will supply study drug as matching 30ml/bottle, labeled for a blinded study. 
 • Test Drug: B244, 30ml/bottle (AOBiome, LLC) • Placebo: Vehicle, 30ml/bottle (AOBiome, LLC) 	

Duration of Patient Study Participation	Up to 84 ± 2 days
Study Endpoints	
PRIMARY
 
 The primary safety endpoint is to assess the safety and tolerability of B244 applied twice daily (BID) to the face for 8 weeks in subjects with mild to moderate rosacea based on the number of AE & SAE. 
EXPLORATORY
 
To assess the efficacy of B244 in subjects with mild to moderate rosacea.
 
 Change of IGA score at Baseline to Week 1, Week 4, Week 8 and Week 12 Change of CEA score at Baseline to Week 1, Week 4, Week 8 and Week 12. Change of PSA score at Baseline to Week 1, Week 4, Week 8 and Week 12. Change of Skindex 16 patient reported outcome from Baseline to Week 1, Week 4, Week 8 and Week 12 IGA treatment success, defined as “clear” or “almost clear” with a 2-grade improvement in IGA score from baseline to the end of treatment. CEA treatment success, defined as “clear” or “almost clear” with a 2-grade improvement in CEA score from baseline to the end of treatment

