10.1.3 Safety

Display Number	Title	Population	Unique/Repeat
14.3.1	Overall Summary of Treatment Emergent Adverse Events	Safety	Unique
14.3.1.1	Summary of Treatment Emergent Adverse Events by System Organ Class and Preferred Term	Safety	Unique
14.3.1.2	Summary of Treatment Emergent Adverse Events by System Organ Class, Preferred Term and Severity	Safety	Repeat
14.3.1.3	Summary of Treatment Emergent Adverse Events by System Organ Class, Preferred Term and Relationship to Study Drug	Safety	Repeat
14.3.2	Summary of Serious Adverse Events by System Organ Class and Preferred Term	Safety	Repeat
14.3.3	Summary of Deaths	Safety	Unique

Table 14.3.1
 Overall Summary of Treatment Emergent Adverse Events.
 Safety Population

	Statistics	B244 Topical Spray n (%)	Placebo n (%)	All Patients n (%)
Total Number of TEAEs	N	xx	xx	xx
Total Number of TESAEs	N	xx	xx	xx
Number of Subjects with:				
At Least One TEAE	n (%)	xx (xx.x)	xx (xx.x)	xx (xx.x)
At Least One Related TEAE	n (%)	xx (xx.x)	xx (xx.x)	xx (xx.x)
At Least One Severe (Grade 3) TEAE	n (%)	xx (xx.x)	xx (xx.x)	xx (xx.x)
At Least One TEAE Leading to Discontinuation	n (%)	xx (xx.x)	xx (xx.x)	xx (xx.x)
At Least One TEAE Leading to Death	n (%)	xx (xx.x)	xx (xx.x)	xx (xx.x)
At Least One TESAE	n (%)	xx (xx.x)	xx (xx.x)	xx (xx.x)
At Least One Related TESAE	n (%)	xx (xx.x)	xx (xx.x)	xx (xx.x)

Protocol: RB244-001
 Confidential

STATISTICAL ANALYSIS PLAN

 Version 2
 02-Apr-19

NOTE: The percentages are based on the number of Safety Population.

Snapshot Data DD-MMM-YYYY

CRF pages

Source: <Dataset>

Program Name: <Pgm name>

Table 14.3.1.1
 Overall Summary of Treatment Emergent Adverse Events by System Organ Class and Preferred Term
 Safety Population

	Statistics	B244 Topical Spray n (%)	Placebo n (%)	All Patients n (%)
Total Number of TEAEs	n	xx	xx	xx
Number of Subjects with at Least One TEAE	n (%)	xx (xx.x)	xx (xx.x)	xx (xx.x)
System Organ Class #1	n (%)	xx (xx.x)	xx (xx.x)	xx (xx.x)
Preferred Term #1	n (%)	xx (xx.x)	xx (xx.x)	xx (xx.x)
Preferred Term #2	n (%)	xx (xx.x)	xx (xx.x)	xx (xx.x)
Preferred Term #3	n (%)	xx (xx.x)	xx (xx.x)	xx (xx.x)
etc.				
System Organ Class #2	n (%)	xx (xx.x)	xx (xx.x)	xx (xx.x)
Preferred Term #1	n (%)	xx (xx.x)	xx (xx.x)	xx (xx.x)
Preferred Term #2	n (%)	xx (xx.x)	xx (xx.x)	xx (xx.x)
Preferred Term #3	n (%)	xx (xx.x)	xx (xx.x)	xx (xx.x)
etc.				

NOTE: The percentages are based on the number of Safety Population.

Snapshot Data DD-MMM-YYYY

CRF pages

Source: <Dataset>

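### The SAP defines a treatment-emergent AE by onset date alone, so a pre-dose AE that worsens after dosing drops out of the TEAE tables if it is kept as one record

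*SAP*

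**What the plan says.** - **TEAE rule.** SAP v2.0 section 6.7.6, identical in v1.0: "Any AE with onset after the first dose of study medication through 56 days after the last dose of study medication". The protocol uses the term TEAE in section 14 without defining it. SAP 8.2.1 adds that AE summaries start with AEs reported from the first dose on Day 1, again without mention of worsening.
- **Collection.** Protocol 12.4: "Adverse Event Collection Period starts with the Screening visit once the ICF has been signed". The protocol synopsis gives the length of that pre-dose period: "Screening period will occur at Days -21 to -1". It includes the washout on Days -14 to -1.
- **Worsening.** Protocol 12.1.1: "Any worsening of a pre-existing condition or illness is considered an AE". It does not say whether the worsening gets its own record and onset date.
- **Separate records.** The only such rule is in the opening paragraph of protocol section 12 and concerns intermittent AEs: "the events must be of similar nature and severity and each intermittent AE will be reported separately". It does not address a rise in severity within a continuing AE.
- **Endpoint and displays.** Safety and tolerability is the only primary objective. The SAP synopsis measures it "in subjects with mild to moderate rosacea based on the number of AE & SAE". Tables 14.3.1 to 14.3.1.3 and AE Listing 16.2.3.1 are all restricted to TEAEs, including the Table 14.3.1 row "At Least One TEAE Leading to Discontinuation".

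**The concern.** An AE that begins in screening or washout and is still present on Day 1 has a known pre-dose onset date. If it becomes more severe on study product and remains the same record, the SAP's test looks at that date, finds it before the first dose, and classifies the event as not treatment-emergent. The on-treatment change is then invisible in the tables that report the primary safety endpoint.

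Aggravation of an existing complaint is a plausible tolerability problem for a spray applied to the face twice daily. The SAP otherwise leans towards capture: a missing severity or relationship takes the worst category (8.2.1), and a completely missing AE start date is set to the first dose (6.7.7). Neither safeguard reaches an AE whose pre-dose onset is known.

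**Working it through.** The documents state no figure that depends on this definition, so there is nothing to reproduce. The check applies the rule to example records and then bounds the size.

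**1. The rule on example dates.** Take the first dose on Day 1 and the last on Day 56. The TEAE window then closes on Day 56 + 56 = Day 112.

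| Record | SAP rule | With a worsening clause |
|---|---|---|
| A. Onset Day -10, worsens Day 20, one record | Not a TEAE (Day -10 precedes Day 1) | TEAE |
| B. Same worsening entered as its own AE, onset Day 20 | TEAE (20 lies between 1 and 112) | TEAE |
| C. Onset Day -10, no worsening | Not a TEAE | Not a TEAE |

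A and B are the same clinical course. Only the recording differs, and the documents do not say which is required.

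**2. Where record A would surface in the SAP v2.0 displays.**

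- *Non-serious, treatment continues:* absent from Tables 14.3.1 to 14.3.1.3 and Listing 16.2.3.1. Section 8.2.1 promises that all reported AEs are listed, but Appendix B names no listing for AEs that are neither treatment-emergent nor serious.
- *Becomes serious:* absent from the treatment-emergent SAE rows of Table 14.3.1. It should appear in Table 14.3.2 and Listing 16.2.3.2, whose titles are not limited to TEAEs.
- *Leads to discontinuation:* absent from the discontinuation row of Table 14.3.1, but counted in disposition Table 14.1.1.2, which has no TEAE filter. SAP section 7 also plans a tabulation and a by-subject listing of discontinuations due to AEs.

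The main loss is therefore the first case.

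**3. Size, on assumed rates.** Protocol 4.2 plans about 130 subjects at 1:1, so 130 / 2 = 65 per arm. The number moved into the TEAE tables is

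65 × (share with a pre-dose AE) × (share of those that worsen on product and stay one record).

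Neither share is in the documents.

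- Shares of 2% to 10% and 10% to 50%: 65 × 0.02 × 0.10 = 0.13, up to 65 × 0.10 × 0.50 = 3.25.
- Shares of 5% to 15% and 10% to 30%: 65 × 0.05 × 0.10 = 0.33, up to 65 × 0.15 × 0.30 = 2.93.

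Both ranges run from a fraction of a subject to about three per arm. These are upper figures for the count of subjects with any TEAE, because a subject with another TEAE is already counted there.

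**The case against.** The strongest reply is that the protocol already deals with this. Section 12.1.1 makes worsening an AE in its own right, and section 12 requires every AE to have an onset date, so a worsening after dosing would carry a post-dose onset and meet the SAP rule. A complaint ongoing on Day 1 is pre-existing relative to the product. The intermittent-event rule, which groups only events of similar severity, leans the same way. Detailed entry instructions normally sit with the eCRF, to which the SAP introduction refers the reader and which is not among the documents reviewed.

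Much of this stands. It means a reader should not infer that such events are certain to be left out: they drop out only when kept as one record. It does not settle the matter. Protocol 12.4 treats as past medical history only what occurred before Screening, so a complaint that began in screening already has an AE record, and nothing tells sites to close it and open another. With about eight or nine sites (protocol 4.2, SAP 4.3), the count depends on an unwritten convention.

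A reader might also infer that the loss falls on B244. The documents do not support that: the rule is the same in both arms and recording is blinded. The loss would be unequal only if one product caused more worsening than the other. Washout-related stinging is a tempting example, but 12.1.1 separately provides that new or worsening rosacea signs and symptoms are recorded as AEs when the investigator believes them related to the product, so part of that ground is covered.

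**Conclusion.** The concern holds in a conditional form. SAP v2.0 section 6.7.6 has an onset-only rule, pre-dose AEs are collected, and no recording rule for worsening is given. A pre-dose AE kept as one record therefore loses its on-treatment worsening from the TEAE tables and the TEAE listing, in either arm.

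The size is unknown and probably a few subjects per arm at most. That judgement rests on the assumed shares in the working. A reader might set the upper figure of 2.93 against 65 × 0.16 = 10.4 subjects with a TEAE, taking the 16% quoted in protocol 1.2.1 from the elevated-blood-pressure trial, and infer a loss of up to 28%. That percentage should not be used. The numerator is assumed, the 16% comes from a different population, and missed events are treated as missed subjects.

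The correction is still worth making, because it concerns the count for the only primary objective and is almost free.

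**What to change.** In SAP v2.0 section 6.7.6, define a TEAE as an AE with onset at or after the first dose, or an AE present before the first dose that increases in severity, becomes serious or leads to discontinuation after it, keeping the existing end of the window. Tabulate the second kind at its post-dose severity.

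State in the eCRF completion instructions that worsening after the first dose is dated as its own onset. If the eCRF cannot change, review all AEs ongoing at Day 1 for worsening before unblinding and flag those that qualify.

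The cost is one SAP sentence, one extra derivation and one entry instruction or blinded review. TEAE counts may rise slightly in both arms.

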6.7.7 Missing Start and Stop Dates for Adverse Events

Start date:

- If start date is completely missing, start date is set to date of first dose.

-
- If (year is present, and month and day are missing) or (year and day are present, and month is missing):
 - If year = year of first dose, then set month and day to month and day of first dose.
 - If year < year of first dose, then set month and day to December 31st.
 - If year > year of first dose, then set month and day to January 1st.
 - If month and year are present and day is missing:
 - If year = year of first dose and
 - If month = month of first dose, then set day to day of first dose date.
 - If month < month of first dose, then set day to last day of month.
 - If month > month of first dose, then set day to 1st day of month.
 - If year < year of first dose, then set day to last day of month.
 - If year > year of first dose, then set day to 1st day of month.

Stop date:

If the outcome of the AE was ongoing or unknown, then the rules outlined below will not be applied.

- If stop date is completely missing, stop date is set to date of study discontinuation.
- If (year is present, and month and day are missing) or (year and day are present, and month is missing):
 - If year = year of study discontinuation, then set month and day to month and day of study discontinuation.
 - If year < year of study discontinuation, then set month and day to December 31st.
 - If year > year of study discontinuation, then set month and day to December 31st.
- If month and year are present and day is missing:
 - If year = year of study discontinuation and
 - If month = month of study discontinuation, then set day to day of study discontinuation date.
 - If month < month of study discontinuation, then set day to last day of month.
 - If month > month of study discontinuation, then set day to last day of month.
 - If year < year of study discontinuation, then set day to last day of month.
 - If year > year of study discontinuation, then set day to last day of month.

7 DATA ANALYSES

The data analysis will be conducted on all participant data when the trial ends. Subjects will be pooled across all sites. Data will be presented by treatment group and overall. Categorical variables will be summarized by frequency distributions (number and percentages of subjects) and continuous variables will be summarized by descriptive statistics (mean, standard deviation, etc.).

Adverse events will be summarized by treatment group using the Medical Dictionary for Regulatory Activities (MedDRA) system organ class and preferred term. Separate tabulations will be produced for all treatment-emergent AEs (TEAEs), treatment-related AEs (those considered by the Investigator as at least possibly drug related), SAEs, discontinuations due to AEs, and AEs Grade 3 severity. By-subject listings will be provided for any deaths, SAEs, and AEs leading to discontinuation.

Descriptive statistics for each treatment group will be provided for clinical laboratory values (e.g., hematology, serum chemistry, and urinalysis) and vital signs data, presented as both actual values and changes from baseline relative to each on-study evaluation. Abnormal clinical laboratory values will be listed.

All data will be provided in by-subject listings.

